2 STUDY OVERVIEW

This is a Phase 2a, multi-site, randomized, parallel-group, placebo-controlled, double-blind, repeated-dose study to evaluate the safety and efficacy of three oral dose levels of HU6 compared to placebo over the course of 61 days in subjects with high body mass index (BMI) and evidence of elevated liver fat.

Subjects will be screened over a 45-day period to determine eligibility based on specific history, physical, laboratory and imaging evaluations. Due to scheduling of the procedures, multiple visits will likely be necessary to complete the screening process. However, if all screening assessments and procedures, including the magnetic resonance imaging (MRI), can be completed within 30 days of the first dose, then a single screening visit is permissible.

Once qualified, subjects will be randomly assigned to one of the HU6 treatment groups or the matched placebo control group and dosed once daily (QD) in a fasting state for a total of 61 days. Subjects will return to the clinic for frequent assessment visits during the 61 days of dosing. A follow-up visit will occur within 10 to 14 days following the completion of dosing (Figure 1).

Figure 1: Study Schematic

10 Visits, Screening, Baseline/First dose, Day 2, Day 7, Day 14, Day 28, Day 42, Day 49, Day 61 / end of treatment, and Follow up at Day 71 – 75.

Visit procedures include PK and PD measures and safety assessments.

Subjects will be instructed to maintain their same diet and activity/exercise level throughout the study as they had prior to participation in the study.

Dosing will take place once daily in a fasted state. Eligible subjects will be randomized equally (N = 20 per group) to 1 of 4 treatment groups:

- Group 1: matched placebo orally once daily for 61 days.
- Group 2: 150 mg HU6 orally once daily for 61 days.
- Group 3: 300 mg HU6 orally once daily for 61 days.
- Group 4: 450 mg HU6 orally once daily for 61 days.

The randomization will be blocked and stratified by HbA_{1c} . Subjects will be stratified into two HbA_{1c} strata: one subgroup of subjects with normal baseline HbA_{1c} defined as HbA_{1c} <5.7% and the other subgroup of subjects with high baseline HbA_{1c} defined as HbA_{1c} between 5.7% and 9.0% inclusive).

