5.2 Summarization of Data

Study results will be summarized by treatment group (i.e., 150 mg QD, 300 mg QD, 450 mg QD, and Placebo) in tabular format with descriptive statistics and/or in subject listings.

For placebo-corrected results, at each visit, the average placebo mean change from baseline will be subtracted from each subject's mean change from baseline.

Statistical testing will be 2-sided and performed using a significance (alpha) level of 0.05. There will be no adjustment for multiple comparisons for this exploratory study.

No imputation of missing data will be performed. No windowing of visits will be performed unless otherwise specified.

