11 EFFICACY ANALYSES

The primary efficacy endpoint will be the reduction in liver fat content measured by the relative change from baseline, as assessed by MRI-PDFF at Day 61. The hypotheses of interest are 2-sided tests comparing each active HU6 treatment group to the placebo group.

```
\begin{split} H_{01} \colon & \mu_{placebo} = \mu_{HU6 \; 150mg} \text{vs} \; H_{11} \colon \mu_{placebo} \neq \mu_{HU6 \; 150mg} \\ & H_{02} \colon \mu_{placebo} = \mu_{HU6 \; 300mg} \text{vs} \; H_{12} \colon \mu_{placebo} \neq \mu_{HU6 \; 300mg} \\ & H_{03} \colon \mu_{placebo} = \mu_{HU6 \; 450mg} \text{vs} \; H_{13} \colon \mu_{placebo} \neq \mu_{HU6 \; 450mg} \end{split}
```

Summary statistics (n, mean, standard deviation, minimum, median, and maximum) will be presented for the observed values for MRI-PDFF at each time point for the FAS population, as described in Section 5.2, Summarization of Data. Summary statistics will also be presented for the change-from-baseline values to each postbaseline time point as well as placebo-corrected change-from-baseline values to each postbaseline time point. In these displays, baseline will be defined as the last non-missing value prior to first dose of study medication. Figures will be generated appropriate to the data output.

Mean change from baseline in liver fat content will be analyzed for the FAS population using an analysis of covariance (ANCOVA) model, including treatment group, HbA_{1c} stratification (normal range versus between 5.7% and 9.0% inclusive) and baseline liver fat from MRI-PDFF as fixed effects. This estimand will include available MRI-PDFF evaluations that occur before discontinuation of treatment. The difference in LS Means for the change from baseline, corresponding 95% CIs, and P values will be provided to assess the treatment differences between placebo and each HU6 treatment group. A separate comparison of the combined HU6 groups and placebo may be conducted.

Responder status (n, %) at Day 61 will be presented. A subject will be deemed a responder if their MRI-PDFF showed a 30% or more reduction from baseline at Day 61. Additional exploratory analysis may be performed such as a different threshold then the 30% or more reduction from baseline due to the short duration of the study.

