The above summary statistics, an ANCOVA model including treatment group and the baseline score of the response variable as fixed effects, and the responder status will also be presented for the subjects randomized only to the HbA1c between 5.7% and 9.0% subgroup.

All MRI-PDFF results will be displayed in subject listings.

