12 PHARMACODYNAMICS ANALYSES

For each pharmacodynamic variable, summary statistics (n, mean, standard deviation, minimum, median, and maximum) will be presented for the observed values at each time point for the FAS population, as described in Section 5.2, Summarization of Data. Summary statistics will also be presented for the change-from-baseline values to each postbaseline time point. For glycated albumin, placebo-corrected change-from-baseline values to each postbaseline time point will be presented. In these displays, baseline will be defined as the last non-missing value prior to first dose of study medication. Figures will be generated appropriate to the data output.

For pharmacodynamic variables with only a Day 61 post-baseline assessment [i.e., ELF variables, HbA_{1c}, abdominal MRI [liver volume, VAT, and SAT], and Fibroscan [Steatosis/VCTE and Fibrosis/CAP], summary statistics will be presented for the change-from-baseline values for each variable at Day 61. Placebo-corrected change-from-baseline values at Day 61 will be presented for abdominal MRI [liver volume, total visceral adipose tissue (VAT) and subcutaneous adipose tissue (SAT)], and Fibrosis/CAP. The ELF variables will be ELF score, hyaluronic acid, procollagen III amino-terminal peptide (PIIINP), and tissue inhibitor of matrix metalloproteinase 1 (TIMP-1). Figures will be generated appropriate to the data output.

For each pharmacodynamic variable with only a Day 61 post-baseline assessment, mean change from baseline will be analyzed for the FAS population using an ANCOVA model, including treatment group, HbA_{1c} stratification (normal range versus between 5.7% and 9.0% inclusive) and the baseline score of the response variable as fixed effects. The difference in LS Means for the change from baseline, corresponding 95% CIs, and P values will be provided to assess the treatment differences between placebo and each HU6 treatment group.

For the abdominal MRI liver volume and adiposity, the above summary statistics, an ANCOVA model including treatment group and the baseline score of the response variable as fixed effects, and the responder status will also be presented for the subjects randomized only to the HbA1c between 5.7% and 9.0% subgroup.

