Continuous pharmacodynamic endpoints with repeated post-baseline assessments [changes from baseline in ApoB, Lp(a), glycated albumin, hs-CRP, liver panel parameters (total cholesterol, HDL, calculated LDL, VLDL, triglycerides, and FFA), HOMA-IR Calc (i.e., the average of the 3 blood draws 5 minutes apart at each scheduled visit), body weight (via InBody Scale), and fasting blood glucose] will be analyzed for the FAS population using a mixed model for repeated measures (MMRM). The estimand will include available post-baseline response data that occur before discontinuation of treatment. The baseline score will be included as the covariate, and HbA_{1c} stratification, treatment group, visit, and the interaction between treatment group and visit will be estimated based on the LSMeans from the MMRM.

For body weight, a responder status (n, %) at Day 61 will be presented. A subject will be deemed a responder if their body weight showed a 1% or more reduction from baseline at Day 61. Additional exploratory analysis may be performed.

In addition, for body weight, the above summary statistics, an MMSE analysis and the responder status will also be presented for the subjects randomized only to the HbA1c between 5.7% and 9.0% subgroup. For the MMRM, the baseline score will be included as the covariate, and treatment group, visit, and the interaction between treatment group and visit will be estimated based on the LSMeans from the MMRM.

All pharmacodynamic results will be displayed in subject listings.

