13.4 InBody Scale Measurements

Summary statistics (n, mean, standard deviation, minimum, median, and maximum) will be presented for the observed values for InBody scale measurements (i.e., total body water, lean body mass, percent body fat, body fat mass, skeletal muscle mass, dry lean mass, and visceral fat) at each time point for the safety population, as described in Section 5.2, Summarization of Data. Summary statistics will also be presented for the change-from-baseline values to each postbaseline time point as well as placebo-corrected change-from-baseline values to each postbaseline time point. In these displays, baseline will be defined as the last non-missing value prior to first dose of study medication. Figures will be generated appropriate to the data output.

For body fat mass and lean body mass, a responder status (n, %) at Day 61 will be presented. A subject will be deemed a responder if their body fat mass showed a 1% or more reduction from baseline at Day 61. The same criteria will be used for the lean body mass. Additional exploratory analysis may be performed.

The responder status will also be presented for the subjects randomized only to the HbA1c between 5.7% and 9.0% subgroup.

InBody measurement results will be listed.

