18 REVISIONS TO STATISTICAL ANALYSIS PLAN

Date	Revision
03 September 2021	The SAP was revised to analyze the HOMA-IR Calc only (i.e., the average of the 3 blood draws 5 minutes apart at each scheduled visit). Insulin, glucose, and C-peptide results will be listed only.
02 December 2021	Added summary statistics for placebo-corrected change-from-baseline values to each postbaseline time point for specified parameters and figures will be generated appropriate to the data output. Added responder status summary statistics for specified parameters at Day 61.
09 December 2021	For subjects in HbA1c 5.7% - 9.0% subgroup only, added summary statistics for change-from-baseline values to each postbaseline time point for specified parameters, placebo-corrected change-from-baseline values to each postbaseline time point for specified parameters, and MMRM or ANCOVA analysis as appropriate. Figures will be generated appropriate to the data output. In addition, added responder status summary statistics for specified parameters at Day 61. An addition, a criterion on body weight was added to the definition of Full Analysis Set (FAS).

16

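### The SAP reports stratum results for HbA1c 5.7-9.0% only, with no HbA1c <5.7% counterpart and no treatment-by-stratum estimate, so it cannot show whether the effect differs by stratum

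*SAP*

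**What the plan says.** Protocol 5.3 and SAP 2 stratify the randomisation by HbA1c. In the SAP, "Subjects will be stratified into two" strata: below 5.7%, and 5.7% to 9.0% inclusive.

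Separate stratum output appears in four places, each time for the upper stratum alone:

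- **MRI-PDFF (SAP 11).** The summary statistics, an ANCOVA and the responder status "will also be presented for the subjects randomized only to the HbA1c between 5.7% and 9.0% subgroup".
- **Abdominal MRI (SAP 12).** "For the abdominal MRI liver volume and adiposity, the above summary statistics, an ANCOVA model including treatment group" and the baseline value, plus responder status, for the same stratum.
- **Body weight (SAP 12).** Summaries, "an MMSE analysis and the responder status will also be presented for the subjects randomized only to the HbA1c between 5.7% and 9.0% subgroup". The next sentence describes an MMRM, so MMSE is presumably a slip.
- **InBody fat mass and lean mass (SAP 13.4).** "The responder status will also be presented for the subjects randomized only to the HbA1c between 5.7% and 9.0% subgroup".

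The primary ANCOVA in SAP 11 contains treatment, HbA1c stratum "and baseline liver fat from MRI-PDFF as fixed effects". It has no treatment-by-stratum term. The pharmacodynamic models in SAP 12 have none either; the only interaction they name is treatment by visit.

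The revision log (SAP 18) records the addition on 09 December 2021: "For subjects in HbA1c 5.7% - 9.0% subgroup only, added summary statistics". Protocol section 12 plans no subgroup analysis.

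**The concern.** An effect that is significant in one stratum is not thereby shown to be specific to it, or larger there. That takes a comparison between strata, which means an estimate of the treatment-by-stratum interaction with its uncertainty. The SAP will put upper-stratum estimates next to the overall ones and show nothing for HbA1c below 5.7%. A reader who sees a significant upper-stratum result will tend to conclude that the drug works in these subjects in particular, and the planned output gives no means of testing that.

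One-sided reporting also leaves the sponsor open to a charge of selection. The addition is dated 09 December 2021, and protocol 5.4 expected the last subject to finish in September 2021. Neither document gives the actual completion, database-lock or unblinding date, so they do not show whether the stratum was chosen before or after unblinding.

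**Working it through.** **Inputs from the documents.** SAP 5.3: 17 evaluable per group, a 30-point difference in mean relative change, SD 30. SAP 5.2: "Statistical testing will be 2-sided and performed using a significance (alpha) level of 0.05", with no multiplicity adjustment. SAP 2: four arms, equal allocation.

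**Assumption.** The documents do not give the share of subjects in the upper stratum. I use 30-70%, equal across arms, which is 5 to 12 of 17 per arm. The baseline covariate is ignored.

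**The plan's own figure.** Two-sample t-test, noncentral t, SE = 30·√(2/17) = 10.3, 32 df: power is 80.7% at 17 per group and 78.1% at 16. The stated 80% at 17 reproduces. With the variance pooled over all four arms (64 df), as in a single model, power is 81.9% and the 95% CI half-width is 1.998 × 10.29 = 20.6 points.

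**Within one stratum.** With n per arm, SE = 30·√(2/n), df = 4n − 4, half-width = t(0.975, df) × SE. At n = 5: SE = 18.97, t(16 df) = 2.120, half-width 40.2.

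**Same true effect (30 points) in both strata.** The strata contain different subjects, so the two tests are independent. Write U and L for power in the upper and lower stratum.

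- Upper only significant: U(1 − L).
- Exactly one significant: U(1 − L) + L(1 − U).

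| n per arm, upper / lower | Upper half-width | U | L | Upper only | Exactly one |
|---|---|---|---|---|---|
| 5 / 12 | 40.2 | 0.318 | 0.669 | 0.106 | 0.561 |
| 8 / 9 | 30.7 | 0.489 | 0.539 | 0.225 | 0.501 |
| 9 / 8 | 28.8 | 0.539 | 0.489 | 0.276 | 0.501 |
| 12 / 5 | 24.7 | 0.669 | 0.318 | 0.456 | 0.561 |

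For 5 / 12, upper only is 0.318 × (1 − 0.669), or about 0.11.

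**Interaction, one dose against placebo.** SE = 30·√(2/a + 2/b), where a and b are the per-arm numbers in the two strata, with 68 − 8 = 60 df.

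- 8 / 9: SE = 20.6, half-width 41.2, power for a true 30-point difference between strata 29.9%.
- 5 / 12: SE = 22.6, half-width 45.2, power 25.7%.

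**False positives on the primary endpoint, by simulation under no effect.** At least one of the three overall tests is significant in about 12.4% of trials. Adding three upper-stratum tests at 0.05 raises this to 21.4% (n = 5), 20.2% (8), 19.9% (9) or 18.2% (12). Testing the stratum contrasts at 0.05 is inferred from SAP 5.2; the subgroup text in section 11 does not mention P values. The 12.4% comes from the unadjusted overall comparisons, not from this addition.

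**The case against.** The SAP nowhere claims that the effect is specific to, or larger in, the upper stratum. The effect in subjects with HbA1c 5.7-9.0% is a legitimate question, the stratum was a randomisation factor, and the comparison within it needs no interaction term to be valid. That is right. The gap lies in what the output can support and what it invites readers to infer.

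The study is called exploratory, the log dates the addition openly, and the subject listings would let someone work out crude lower-stratum values. These points soften the problem. They do not supply a lower-stratum model or an interaction estimate. The permission in SAP 11 for further exploratory analysis gives a different responder threshold as its example and commits to no comparison of strata.

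The exactly-one-stratum figure (50-56%) includes trials where only the lower stratum is significant, which the planned output would not show. For the SAP as written, 11-46% is the relevant range. The baseline covariate could also reduce the residual SD. At an assumed SD of 26, upper-stratum power is 40-79% rather than 32-67%, while upper-only significance is about 9-47%, so the argument is unchanged.

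The interaction will be imprecise, and a repeated-measures model with few subjects per arm may be hard to fit. The first is true and should be stated. The second applies equally to the upper-stratum weight model already planned.

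**Conclusion.** The concern holds. Followed as written, the SAP gives one-sided stratum reporting that cannot show whether the treatment effect differs by HbA1c. The upper-stratum contrast itself is a valid but imprecise randomised comparison: 95% CI half-width about 25 to 40 points against 21 overall, and power 32-67% against 82%. With no difference between strata, a dose would still look effective in the upper stratum alone in 11-46% of trials.

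These figures rest on the assumed 30-70% share, SD 30, 17 evaluable per arm and no baseline adjustment. The qualitative point does not depend on the share, because 17 per arm are being split in two. The primary analysis is unaffected, and the documents do not establish a data-driven choice of stratum. This should be corrected, but it does not undermine the trial.

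**What to change.** - Wherever the SAP plans upper-stratum output (sections 11, 12 and 13.4), present the same summaries, ANCOVA or MMRM, and responder rates for both randomisation strata side by side.
- Leave the main-effects primary model as it is. Add one supplementary model with a treatment-by-stratum term, and report the interaction estimate for each dose with its 95% CI.
- Label all stratum results as exploratory and added after the protocol, and state that no claims will be based on stratum P values.
- Say in advance that the interaction interval is expected to be about ±41 to 45 points per dose, with 26-30% power for a true 30-point difference between strata (under the assumptions above). Its main use is to show openly that the trial cannot settle the question.

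The cost is SAP wording, a second set of existing tables and one extra model. The stratum is already a model term, so no new data are needed.

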12 PHARMACODYNAMICS ANALYSES

For each pharmacodynamic variable, summary statistics (n, mean, standard deviation, minimum, median, and maximum) will be presented for the observed values at each time point for the FAS population, as described in Section 5.2, Summarization of Data. Summary statistics will also be presented for the change-from-baseline values to each postbaseline time point. For glycated albumin, placebo-corrected change-from-baseline values to each postbaseline time point will be presented. In these displays, baseline will be defined as the last non-missing value prior to first dose of study medication. Figures will be generated appropriate to the data output.

For pharmacodynamic variables with only a Day 61 post-baseline assessment [i.e., ELF variables, HbA_{1c}, abdominal MRI [liver volume, VAT, and SAT], and Fibroscan [Steatosis/VCTE and Fibrosis/CAP], summary statistics will be presented for the change-from-baseline values for each variable at Day 61. Placebo-corrected change-from-baseline values at Day 61 will be presented for abdominal MRI [liver volume, total visceral adipose tissue (VAT) and subcutaneous adipose tissue (SAT)], and Fibrosis/CAP. The ELF variables will be ELF score, hyaluronic acid, procollagen III amino-terminal peptide (PIIINP), and tissue inhibitor of matrix metalloproteinase 1 (TIMP-1). Figures will be generated appropriate to the data output.

For each pharmacodynamic variable with only a Day 61 post-baseline assessment, mean change from baseline will be analyzed for the FAS population using an ANCOVA model, including treatment group, HbA_{1c} stratification (normal range versus between 5.7% and 9.0% inclusive) and the baseline score of the response variable as fixed effects. The difference in LS Means for the change from baseline, corresponding 95% CIs, and P values will be provided to assess the treatment differences between placebo and each HU6 treatment group.

For the abdominal MRI liver volume and adiposity, the above summary statistics, an ANCOVA model including treatment group and the baseline score of the response variable as fixed effects, and the responder status will also be presented for the subjects randomized only to the HbA1c between 5.7% and 9.0% subgroup.

Continuous pharmacodynamic endpoints with repeated post-baseline assessments [changes from baseline in ApoB, Lp(a), glycated albumin, hs-CRP, liver panel parameters (total cholesterol, HDL, calculated LDL, VLDL, triglycerides, and FFA), HOMA-IR Calc (i.e., the average of the 3 blood draws 5 minutes apart at each scheduled visit), body weight (via InBody Scale), and fasting blood glucose] will be analyzed for the FAS population using a mixed model for repeated measures (MMRM). The estimand will include available post-baseline response data that occur before discontinuation of treatment. The baseline score will be included as the covariate, and HbA_{1c} stratification, treatment group, visit, and the interaction between treatment group and visit will be estimated based on the LSMeans from the MMRM.

For body weight, a responder status (n, %) at Day 61 will be presented. A subject will be deemed a responder if their body weight showed a 1% or more reduction from baseline at Day 61. Additional exploratory analysis may be performed.

In addition, for body weight, the above summary statistics, an MMSE analysis and the responder status will also be presented for the subjects randomized only to the HbA1c between 5.7% and 9.0% subgroup. For the MMRM, the baseline score will be included as the covariate, and treatment group, visit, and the interaction between treatment group and visit will be estimated based on the LSMeans from the MMRM.

All pharmacodynamic results will be displayed in subject listings.

13 SAFETY ANALYSES

13.1 Adverse Events

Adverse events will be coded using the MedDRA coding system (using MedDRA Version stated in Data Management Plan). An overall summary table will be presented to summarize all

treatment-emergent AEs (TEAEs), all treatment-emergent study drug-related AEs, all severe TEAEs, deaths, all serious TEAEs, and all study drug discontinuations due to TEAEs for all subjects in the safety population as described in Section 5.2, Summarization of Data. In addition, frequency tables will present all TEAEs by System Organ Class and Preferred Term and study drug-related TEAEs by System Organ Class and Preferred Term, with a separate display of study-drug related TEAEs by maximum severity for all subjects in the safety population.

If an AE occurs after the informed consent form has been signed and before the time of the first dose of study drug, it will be considered a pretreatment AE. If an AE occurs at the time of or after the first dose of study drug or if the pretreatment AE worsens, it will be considered a treatment-emergent AE.

If the relationship to study medication is missing, it will be assumed to be related to study medication for analysis purposes.

In all displays, AEs will be displayed by MedDRA System Organ Class and Preferred Term, with subjects who have the same AE counted only once for that event and subjects who have more than one AE within a System Organ Class counted only once in that System Organ Class.

